## 9 DRUG MANAGEMENT

### 9.1 Drug supplies

Commercial esomeprazole (Nexium) tablets are supplied by AstraZeneca free of charge for a period of 8 or 10 years (if the patients re-consented) from the date of each patient's randomisation or until 28th February 2017 (we will allow +3 months for appointment slippage). The last delivery of study drug will be on or around 31st August 2016. Esomeprazole is supplied in blister packs of 2 x 28 tablets.

Aspirin should be supplied by the local hospital pharmacy. There is no specification on the brand of aspirin, although soluble aspirin should be supplied wherever possible.

Patients are requested to come to the hospital pharmacy every 6 months to return unused medication and pick up a new 6-month supply. In some cases where this is not possible, special dispensation by the local research team may allow the medication to be posted as per local procedures. However, there is no central funding available to cover postage costs.

### 9.2 Drug ordering

The Trial Office will calculate the quantity of 20mg and 40mg esomeprazole required for the year based on the number of patients taking each dose (20mg/40mg/80mg). The Trial Office will order the IMP and Astra Zeneca will deliver the IMP to the hospital on a 6-monthly basis until 31st August 2016. Ad hoc drug orders are not possible.

### 9.3 IMP Receipt

Upon receipt of trial medication, a fax-back confirmation form (included in the delivery) included in the delivery, must be signed and faxed from the hospital pharmacy to the Trial Office [contact]

If supplies are damaged on arrival, contact the Trial Office. Damaged supplies should be destroyed on site and a Drug Destruction Form completed and a copy forwarded to the Trial Office by Fax or email.

#### **9.4 Handling and storage**

Esomeprazole should not be stored above 30°C. There is no minimum storage temperature specified, although Astra Zeneca have confirmed that the drug remains stable at sub-zero temperatures. Store in the original package (blister). Esomeprazole has a shelf life of 3 years. Aspirin should be stored in a dry place below 25°C. Aspirin has a shelf life of 3 years.

#### **9.5 Labelling**

The responsible Pharmacy will ensure that IMP supplies dispensed for trial use are appropriately labelled in accordance with all applicable regulatory requirements.

Labelling of trial esomeprazole is to be carried out by the site pharmacies. MHRA approved labels for esomeprazole for clinical trial use will be supplied by the Trial Office.

MHRA approved labels for aspirin for clinical trial use are not required and labels for aspirin will not be supplied by the Trial Office. Aspirin must be labelled as per normal dispensing requirements.

#### **9.6 Dosing dispensing**

Both esomeprazole and aspirin should be dispensed from the participating hospital's pharmacy every six months (from date of first trial prescription).

#### **9.7 Drug accountability**

Participating pharmacies must maintain a Dispensing and Returns Log to document all aspirin and esomeprazole dispensed to trial participants. This Log must be available for inspection by AspECT staff and the MHRA if required. Each Dispensing and Returns Log must be copied and the original returned to the Trial Office once the patient has completed their treatment. The photocopy must be retained in the Pharmacy File.

#### **9.8 Drug returns from patients**

Patients must return unused tablets to their local trial pharmacy for accountability and compliance checks.

#### **9.9 Drug destruction**

Unused drugs must be destroyed on site as per local practice and a Drug Destruction Form completed. The Drug Destruction Form must be faxed to the Trial Office [contact]

### **10 ASSESSMENT OF SAFETY**

The Investigator must monitor each patient for clinical and laboratory evidence of adverse events at each contact with the participant throughout the study. During the course of the annual Follow Up, all patients should be asked directly if they have had any hospital admissions or events which should be reported as a SAE (see definition in Section 10.1). Their patient notes should also be checked for such occurrences. All SAEs should be reported to the Trial Office as described in Section 10.4.

Adverse event monitoring starts from the time the patient commences study medication until they complete the trial. An SAE which occurs more than 30 days after a patient has stopped taking trial medication is not required to be reported, unless the event is related to a trial procedure (e.g. biopsy or blood collection). All SAEs will be followed to a satisfactory conclusion. Any SAEs that are unresolved at the patient's last visit in the study are followed up by the Investigator for as long as medically indicated.

All SAEs reported to the Trial Office will be processed according to internal SOPs. The Trial Office may request additional information for any SAE as judged necessary.

## 10.1 Adverse event definitions

An Adverse Event or experience (AE) is any untoward medical occurrence in a study subject temporally associated with the administration of an investigational medicinal product (IMP) or a comparator product, whether or not considered related to the IMP or a comparator product. An AE can therefore be any unfavourable and unintended sign, symptom, disease (new or exacerbated) and /or significant abnormal laboratory or physiological observation temporally associated with the use of a medicinal product. For marketed medicinal products, this also includes failure to produce expected benefits (i.e. lack of efficacy), abuse or misuse.

**A Serious Adverse Event (SAE)** is any AE, regardless of dose, causality or expectedness, that:

Results in death	
Is life-threatening	This refers to an event in which the subject was at risk of death at the time of the event. It does not refer to an event, which hypothetically might have caused death, if it were more severe.
Requires in-patient hospitalisation or prolongs existing inpatient hospitalisation	In general, hospitalisation signifies that the subject has been admitted (usually involving at least an overnight stay) at the hospital or emergency ward for observation and/or treatment that would not have been appropriate in the physician's office or out-patient setting. Hospitalisation for a pre-existing condition, including elective procedures, which has not worsened, does not constitute a serious adverse event. Complications that occur during hospitalisation are AEs. If a complication prolongs hospitalisation or fulfils any other serious criteria, the event is serious. When in doubt as to whether hospitalisation occurred or was necessary, the AE should be considered serious.
Results in persistent or significant incapacity or disability	This means a substantial disruption of a person's ability to conduct normal life functions. It does not include experiences of relatively minor medical significance or accidental trauma (e.g. sprained ankle), which do not constitute a substantial disruption.
Is a congenital anomaly or birth defect	
Is any other medically other medically important event	Defined as an event that may jeopardise the patient or may require intervention to prevent one of the outcomes listed above.

**An Adverse Drug Reaction (ADR)** is an AE which is considered to be causally related to any dose of the IMP. This means that a causal relationship between the IMP and the AE is at least a reasonable possibility, i.e. the relationship cannot be ruled out.

**An Unexpected Drug Reaction** is an adverse drug reaction, the nature or severity of which, is not consistent with applicable product information (referring to information in the SmPC or IB).

**A Suspected Unexpected Serious Adverse Drug Reaction (SUSAR)** is a serious adverse drug reaction, the nature or severity of which is not consistent with the applicable product information (e.g. Investigator's Brochure for an unapproved investigational product or SmPC for an approved product).

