9.1 Resource Use and Cost Data

The health economics data for this trial will not be analysed by CSM; the analysis will be undertaken by [name].

10. Exploratory analyses not specified prior to receiving data

Any analyses not specified in this document will be exploratory in nature.

11. Serious adverse events

Serious adverse events are defined as those that are fatal, life threatening, disabling, a congenital birth defect, another important medical event which require hospitalisation or prolongation of hospitalisation. Any serious adverse event occurring whilst a participant is continuing in the study, until trial medication is stopped will be recorded. All serious adverse events will be described in tables including causality, CTCAEgrade, outcome and seriousness. A comparison of specific serious adverse events between the treatment groups (aspirin vs no aspirin and low PPI vs high PPI) will be assessed by examination of 95% confidence intervals for the difference in incidence. An overall category for any serious adverse event will also be compared using the chi square test. The analysis will be conducted by intention to treat. An overall category for renal impairment (dehydration, renal, obstruction) will be compared using the chi square test.

SAE and death major bleeds will be summed and expressed as number of major bleeds per 1000 person years. 2 major bleeds per 10000 person years is expected.

12. Data from Canada

One site in Canada ran a trial of 50 patients using the same protocol. The entire analysis plan will be re-run including this data when it is available.

AspECT

A phase III randomised study of Aspirin and Esomeprazole chemoprevention in Barrett's metaplasia

Funded by CR-UK, MRC, UHL and NCI

ISRCTN No.85156844

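### SAP section 11 merges two separate Protocol 10.1 seriousness criteria into one joint condition; the SAE definition should be aligned before the safety analysis

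*Protocol*

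**What the plan says.** Protocol 10.1 defines an SAE as any adverse event meeting at least one of six criteria. Two matter here. One is "Requires in-patient hospitalisation or prolongs existing inpatient hospitalisation". The other is any other medically important event, explained as "Defined as an event that may jeopardise the patient or may require intervention to prevent one of the outcomes listed above". Each is enough alone.

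SAP section 11 gives its own definition: "Serious adverse events are defined as those that are fatal, life threatening, disabling, a congenital birth defect, another important medical event which require hospitalisation". That sentence runs on to cover prolonged stays, so its last item reads in full "another important medical event which require hospitalisation or prolongation of hospitalisation". Hospitalisation does not appear as a separate item.

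The rest of SAP section 11 uses the defined term. All SAEs are tabulated, with seriousness among the columns. Specific SAEs are compared between arms, and the comparison "will be assessed by examination of 95% confidence intervals for the difference in incidence". For the total, "An overall category for any serious adverse event will also be compared using the chi square test"; a renal category is handled in the same way. For bleeding, "SAE and death major bleeds will be summed and expressed as number of major bleeds per 1000 person years".

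**The concern.** The SAP definition is not the one under which sites report. Protocol section 10 sends all SAEs, as defined in 10.1, to the Trial Office, and Protocol 10.4 requires the reason for seriousness on each report. The narrower SAP set could therefore be extracted from the data if someone chose to apply it.

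The SAP introduction says results should follow the SAP and that deviations must be described and justified. Formally, then, an analyst who used the wider protocol set would be departing from the written definition.

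Little else would catch an event left out:
- Protocol 10.7 records non-serious events only when they lead to withdrawal from study medication.
- SAP section 11 plans no safety comparison other than those built on SAEs and bleeding.
- The independent second analysis in SAP section 5 covers the primary analysis and the first two secondaries, not safety.
- SAP sections 2.7 and 9 take cardiac events from SAE data, so the same definition feeds the cardiac-disease and aspirin-resistance models.

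**Working it through.** No stated figure depends on this definition, so there is nothing to reproduce. The check compares the two texts.

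**Step 1: criteria common to both.** Death, threat to life, disability and congenital anomaly stand alone in both documents. Any event meeting one of these is serious under either, whether or not the patient was admitted.

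**Step 2: the remaining events.** For an event meeting none of those four, let H mean that it required or prolonged hospitalisation, and M that it was medically important. The protocol counts it if H *or* M. The SAP, read literally, counts it if H *and* M.

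| H | M | Protocol 10.1 | SAP section 11, literal |
|---|---|---|---|
| yes | yes | SAE | SAE |
| no | yes | SAE | not an SAE |
| yes | no | SAE | not an SAE |
| no | no | not an SAE | not an SAE |

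The definitions differ in the two middle rows. The second row is an important event managed without admission. The third is an admission that nobody classed as an important medical event; the SAP does not say how that judgement would be made.

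**Step 3: bleeds.** Major bleeds are summed from SAEs and deaths, so a fatal bleed is counted either way. A life-threatening or disabling bleed also stays in. The realistic exposure is a non-fatal major bleed with medical importance as its only criterion and no admission.

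**Step 4: can the exposure be sized?** No. Neither document gives the share of SAEs, or of major bleeds, that falls in the middle rows. For context only, the SAP states that "2 major bleeds per 10000 person years is expected". With 2513 patients (SAP 2.3) and an assumed mean follow-up of 5 to 10 years:

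- 2513 × 5 × 2/10000 = 2.5 major bleeds
- 2513 × 10 × 2/10000 = 5.0 major bleeds

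These are whole-trial expectations at the SAP's own rate. They show that the bleed analysis would rest on few events if that rate held. They do not estimate how many would be lost.

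**The case against.** The strongest reply is that no event is actually dropped. SAEs are collected under Protocol 10.1, the SAP says that all of them are tabulated, and nothing in SAP section 11 re-screens or excludes an SAE already reported and logged. Tabulating by seriousness would display the events at issue rather than remove them.

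The sentence also reads like a faulty paraphrase. It has no conjunction before its last item, and its verb does not agree with its noun. Insert a missing *or* before the hospitalisation clause and the list becomes the protocol's six criteria. SAP 6.6 supports that reading, since it treats a cardiac event as an SAE when it fulfils any one criterion for seriousness.

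The middle rows may also be thinly populated. Protocol 10.1 counts admission for observation as hospitalisation, and says that doubtful cases should be treated as serious.

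Most of this stands. A reader might infer that the SAP already analyses a smaller set, that harm is understated by some percentage, or that the bleed rate is biased downwards. The documents support none of these: there is no exclusion rule and no figure for the events exposed. Nor do they support the inference that open-label admission decisions distort this definition in particular. No text suggests that admission thresholds differ by arm, and the worry would apply equally to the protocol's own hospitalisation criterion.

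What the reply does not remove is the wording. If an *or* was meant, the SAP does not say so, and two analysts could derive different SAE sets from the same database.

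**Conclusion.** The mismatch is real, and it sits in SAP section 11; Protocol 10.1 is complete as it stands. Applied literally, the SAP would omit non-hospitalised events whose sole criterion is medical importance, and hospitalisations not judged important medical events. The omission would reach the SAE tables, the intervals, the chi-square tests and the non-fatal part of the major-bleed count.

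It would be too broad to say that events serious for other reasons in general fall out. Fatal, life-threatening, disabling and congenital events are unaffected, as are fatal bleeds. The number exposed cannot be derived from the documents, and any loss is conditional on literal application. The primary efficacy analysis is untouched. This is a minor alignment, best settled before anyone sees the treatment comparisons.

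**What to change.** In SAP section 11, replace the definition with the six criteria of Protocol 10.1, stated as alternatives, with hospitalisation and other medically important event on separate lines. Add one sentence saying that every SAE reported under Protocol 10.1 enters the SAE tables, the between-arm comparisons and the bleed count.

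The cost is a sentence or two in the SAP. No new data are needed, because sites already report by the protocol definition and record the reason for seriousness.

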## 10.2 Determining adverse event causality

The Investigator will assess and classify the relationship of an AE to the trial IMP as follows:

Classification	Relationship	Definition
----------------	--------------	------------

Drug-related (reasonable possibility)	Definitely Related	
 
Starts within a time related to the study drug administration and
 
No obvious alternative medical explanation.
 

	Probably Related	
 
Starts within a time related to the study drug administration and
 
Cannot be reasonably explained by known characteristics of the patient's clinical state.
 

	Possibly Related	
 
Starts within a time related to the study drug administration and
 
A causal relationship between the study drug and the adverse event is at least a reasonable possibility.
 

No reasonable possibility of being drug related	Probably Not Related	
 
The time association or the patient's clinical state is such that the study drug is not likely to have had an association with the observed effect.
 

	Definitely Not Related	
 
The AE is definitely not associated with the study drug administered.
 

The Investigator must endeavour to obtain sufficient information to confirm the causality of the adverse event (i.e. relation to study drug, other illness, progressive malignancy etc.) and give their opinion of the causal relationship between each AE and study drug. This may require instituting supplementary investigations of significant AEs based on their clinical judgement of the likely causative factors and/or include seeking a further specialist opinion.

### 10.3 Expected adverse events

Section 4.8 of the SmPC for aspirin lists all the expected side effects associated with the use of aspirin. A copy of this document must be held in the Site File for reference.

Section 4.8 of the SmPC for 20mg and 40mg esomeprazole lists all the expected side effects associated with the use of 20mg and 40mg esomeprazole. A copy of this document must be held in the Site File for reference.

For patients receiving the 80mg esomeprazole dose, Section 4.8 of the IB lists all the expected side effects associated with the use of esomeprazole. A copy of this document must be held in the Site File for reference.

A list of the most noteworthy expected side effects known at the time of writing is given below for ease of reference.

#### Aspirin

Side effects are grouped on the basis of System Organ Class. Within each system organ class the frequencies are defined as: very common ( $\geq 1/10$ ), common ( $\geq 1/100$  to  $< 1/10$ ), uncommon ( $\geq 1/1,000$  to  $< 1/100$ ), rare ( $\geq 1/10,000$  to  $< 1/1,000$ ), very rare ( $< 1/10,000$ ) and not known (cannot be estimated from the available data).

#### Aspirin: Undesirable Effects

Blood and lymphatic system disorders	
Common: Increased bleeding tendencies.
 
Rare: Thrombocytopenia, agranulocytosis, aplastic anaemia.
 
Not known:

--------------------------------------	--

	Cases of bleeding with prolonged bleeding time such as epistaxis, gingival bleeding. Symptoms may persist for a period of 4–8 days after acetylsalicylic acid discontinuation. As a result there may be an increased risk of bleeding during surgical procedures. Existing (haematemesis, melaena) or occult gastrointestinal bleeding, which may lead to iron deficiency anaemia (more common at higher doses). anaemia, haemolytic anaemia, hypoprothrombinaemia, pancytopenia, occult blood loss, elevated transaminase levels
Immune system disorders	Rare: Hypersensitivity reactions, angio-oedema, allergic oedema, anaphylactic reactions including shock.
Metabolism and digestive system disorders	Not known: Hyperuricemia.
Nervous system disorders	Rare: Intracranial haemorrhage Not known: Headache, vertigo.
Ear and labyrinth disorders	Not known: Reduced hearing ability; tinnitus.
Vascular disorders	Rare: Haemorrhagic vasculitis.
Respiratory, thoracic and mediastinal disorders	Uncommon: Rhinitis, dyspnoea. Rare: Bronchospasm, asthma attacks.
Reproductive system and mammary disorders	Rare: Menorrhagia
Gastrointestinal disorders	Common: Dyspepsia. Rare: Severe gastrointestinal haemorrhage, nausea, vomiting. Not known: Gastric or duodenal ulcers and perforation which can occasionally be major (may develop bloody or black tarry stools, severe stomach pain and vomiting blood), gastrointestinal irritation (mild stomach pain), erosions, heartburn, Fatalities have occurred.
Hepatobiliary disorders	Not known: Hepatic insufficiency, hepatitis (particularly in patients with SLE or connective tissue disease)
Skin and subcutaneous tissue disorders	Uncommon: Urticaria. Rare: Steven-Johnsons syndrome, Lyells syndrome, purpura, erythema nodosum, erythema multiforme.
Renal and urinary tract disorders	Not known: Impaired renal function
Body as a whole – general disorders	Not known: Salicylism – (mild chronic salicylate intoxication may occur after repeated administration of large doses, symptoms include dizziness, tinnitus, deafness, sweating, nausea, vomiting, headache and mental confusion, and may be controlled by reducing the dose)

### Children

Aspirin may be associated with the development of Reye's Syndrome (encephalopathy and hepatic failure) in children presenting with an acute febrile illness.

## Esomeprazole: Undesirable Effects

	Common (≥1/100)	Uncommon (≥1/1000 and <1/100)	Rare (≥1/10000 and <1/1000)	Very rare <1/10000
Blood and lymphatic system disorders			Leukopenia, thrombocytopenia	Agranulocytosis, pancytopenia
Immune system disorders			Hypersensitivity reactions e.g. angioedema and anaphylactic reaction/shock	
Metabolism and nutrition disorders		Peripheral oedema	Hyponatraemia	Hypomagnesaemia; severe hypomagnesaemia may also result in hypocalcaemia. Hypomagnesaemia may also result in hypokalaemia.
Psychiatric disorders		Insomnia	Agitation, confusion, depression	Aggression, hallucination
Nervous system disorders	Headache	Dizziness*, paraesthesia, somnolence	Taste disturbance	
Eye disorders			Blurred vision*	
Ear and labyrinth disorders		Vertigo		
Respiratory, thoracic and mediastinal disorders			Bronchospasm	
Gastrointestinal disorders	Abdominal pain, diarrhoea, flatulence, nausea/vomiting, constipation	Dry mouth	Stomatitis, gastrointestinal candidiasis	Microscopic colitis
Hepatobiliary disorders		Increased liver enzymes	Hepatitis with or without jaundice	Hepatic failure, hepatic encephalopathy
Skin and subcutaneous tissue disorders		Dermatitis, pruritus, urticaria, rash	Alopecia, photosensitivity	Erythema multiforme, Stevens-Johnson syndrome, toxic epidermal necrolysis (TEN)
Musculoskeletal, connective tissue and bone disorders			Arthralgia, myalgia	Muscular weakness

	Common ( $\geq 1/100$ )	Uncommon ( $\geq 1/1000$ and $< 1/100$ )	Rare ( $\geq 1/10000$ and $< 1/1000$ )	Very rare <1/10000
Renal and urinary disorders				Interstitial nephritis
Reproductive system and breast disorders				Gynaecomastia
General disorders and administration site conditions			Malaise, hyperhidrosis	

\*The SmPC for esomeprazole has been updated with the following: "Esomeprazole has minor influence on the ability to drive or use machines. Adverse reactions such as dizziness (uncommon) and blurred vision (rare) has been reported. If affected patients should not drive or use machines."

